***Secondary Endpoints***

The following secondary efficacy endpoints will be evaluated per investigator assessment:

- ORR, defined as proportion of patients who have achieved confirmed complete response (CR) or partial response (PR), evaluated using RECIST (v.1.1) and iRECIST based on investigator assessment
- DCR, defined as the percentage of patients who have achieved best overall response (BOR) of CR, PR, or SD per RECIST (v.1.1) and iRECIST

- DOR, defined as the time from first documentation of a response (CR or PR) until time of first documentation of disease progression by RECIST (v.1.1) and iRECIST, or death by any cause
- PFS, defined as the time from the date of the first dose of study treatment to the earlier date of assessment of progression by RECIST (v.1.1) and iRECIST, or death by any cause
- 6-month PFS Rate, defined as the proportion of patients who neither progressed by RECIST (v.1.1) and iRECIST nor died before 6 months (24 weeks) from the first study treatment
- OS, defined as the time from the date of the first dose of study treatment to the date of death by any cause
- Safety assessments:
  - AEs assessed according to CTCAE v4.03
  - DLT observed during the first 2 cycles
  - Dose interruption, reduction, and dose intensity per dose administration record
  - The incidence of treatment-emergent AEs (TEAEs) during the first 2 cycles compared with the third and subsequent cycles
  - The incidence of TEAEs occurring while patients are on treatment or up to 30 days after the last dose of study drug
  - The incidence of AEs that occur from signing the ICF until the first dose of treatment
  - The incidence of SAEs occurring while patients are on treatment through 30 days after the last dose of study drug
  - Changes in clinical laboratory parameters (hematology, chemistry, urinalysis), vital signs, ECOG performance status, electrocardiogram (ECG) parameters, physical examinations, and usage of concomitant medications (additional details in the schedule of assessments)

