Cancer vaccines, including neoantigens, are currently being explored in combination with anti-PD-1 and anti-PD-L1 antibodies in several clinical trials with the intent to reinvigorate T cell-mediated tumor killing and enhance the anti-PD-1 effect. However, since the PD-1 pathway plays an important role in the balance of T cell activation and tolerance (Patsoukis N, 2017), identifying the optimal timing or sequencing of PD-1 blockade with respect to T cell receptor (TCR) engagement and the status of T cell priming is essential to achieve maximum therapeutic

[figure not shown]
benefits. In mouse tumor models that are known to be resistant to anti-PD-1 therapy, PD-1 blockade in suboptimally primed CD8+ T cell conditions results in the generation of dysfunctional PD-1+CD38hi CD8+ cells, leading to resistance to anti-PD-1 antibody and therapeutic failure. On the other hand, optimal antigenic stimulation reverses anti-PD-1 resistance. These results suggest that (1) concomitant treatment with anti-PD-1 in suboptimal priming conditions confers resistance to immunotherapy that can be reversed by proper antigen stimulation and (2) appropriate sequencing of immunomodulatory agents is crucial for therapeutic outcomes (Verma, 2019). In addition, Pauken et al. show that constitutive loss of PD-1 during acute infection causes overactivation of CD8+ T cells during the effector phase and impairs memory and recall responses. These data indicate PD-1 is required for optimal memory (Pauken, 2020). Based on the recent finding above, anti-PD-1 antibody therapy will be integrated in a staggered schedule into DSP-7888 Dosing Emulsion from Day 29 (Arm 1) or Day 22 (Arm 2), based on the choice of combination therapy, when optimal priming of WT1-specific CTL by DSP-7888 Dosing Emulsion has been expected.

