#### 6.1.3. Enrichment Part

The Phase 1b enrichment cohort (consisting of the additional 10 patients) will include patients with locally advanced or metastatic RCC or urothelial carcinoma who experienced disease progression per iRECIST (immune confirmed progressive disease [iCPD]) during or within 3 months of last dose of the most recent prior anti-PD-1/PD-L1-based treatment.

Patients will be treated with the combination of DSP-7888 Dosing Emulsion and nivolumab, or DSP 7888 Dosing Emulsion and pembrolizumab, as per the treating physician's choice.

The administration of DSP-7888 Dosing Emulsion and anti-PD1 therapy in the Phase 1b enrichment cohort will differ from that in the Phase 1b dose search part of the study, and will be staggered as follows:

Arm 1 (Enrichment Cohort Only): DSP-7888 + nivolumab combination:

- DSP-7888 Dosing Emulsion will start on Day 1, Q1W for first 4 weeks, then Q2W thereafter
- Nivolumab will start on Day 1 of Cycle 3 (Day 29), Q2W

Arm 2 (Enrichment Cohort Only): DSP-7888 + pembrolizumab combination:

- DSP-7888 Dosing Emulsion will start on Day 1, Q1W for first 3 weeks, then Q3W thereafter
- Pembrolizumab will start on Day 1 of Cycle 2 (Day 22), Q3W

#### 6.1.4. Phase 2

A Phase 2, multicenter, open-label, single-arm, study will be conducted to evaluate the efficacy and safety of DSP-7888 Dosing Emulsion in combination with pembrolizumab in patients with advanced high-grade serous epithelial ovarian, fallopian tube, or primary peritoneal cancer who were previously treated with platinum-based therapy and experienced resistance to platinum-based therapy, defined as patient relapsed within 6 months after last dose of platinum-based therapy. Patients must have received 1 to 4 previous treatment regimens.

The Phase 2 dose of DSP-7888 Dosing Emulsion will be the recommended dose as determined in the Phase 1b Arm 2 part of the study.

Approximately 40 eligible PROC patients are expected to be enrolled in the Phase 2 dose expansion part of the study.

For patients enrolled under Protocol Amendment 4, the administration of DSP-7888 Dosing Emulsion and anti-PD1 in the Phase 2 dose expansion cohort is the same as that in the Phase 1b Arm 2 of the dose search part. For patients enrolled under Protocol Amendment 5, administration of DSP-7888 Dosing Emulsion and anti-PD1 will be staggered as follows:

DSP-7888 + pembrolizumab combination:

- DSP-7888 Dosing Emulsion will start on Day 1, Q1W for first 3 weeks, then Q3W thereafter

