2.2. Statistical Decision Rules

For Phase 2 Cohort Only

There is no formal hypothesis testing for the Phase 2 cohort. A Bayesian decision-making framework will be employed to quantify whether proof of concept (POC) can be established based on the overall response rate (ORR) by Week 24 from the final analysis for the overall population and/or the CPS < 10 subpopulation. The POC is established at the final analysis if either or both of the following 2 conditions are met:

- In the overall population, 70% credible interval of ORR with 10% in the left tail and 20% in the right tail will be calculated: if lower bound $\geq 8\%$ and upper bound $\geq 21\%$ (where 8% is the reference value [Protocol Amend 6, Section 4.3.1; Matulonis, 2019] and 21% is the target value of ORR in the overall population), the study will achieve POC.
- In the CPS < 10 subpopulation, 50% credible interval of ORR with 20% in the left tail and 30% in the right tail will be calculated: if lower bound $\geq 5\%$ and upper bound $\geq 15\%$ (where 5% is the reference value [Protocol Amend 6, Section 4.3.1; Matulonis, 2019] and 15% is the target value of ORR in CPS < 10 subpopulation), the study will achieve POC.

The interim monitoring analysis for futility early efficacy assessment will be conducted using a Bayesian method and will start after the first 20 patients have response evaluation, withdraw, or die by Week 24.

- If the posterior probability of ORR $\geq 21\%$ in the overall population is $\leq 2.5\%$ AND the posterior probability of ORR $\geq 15\%$ in the CPS < 10 subpopulation is $\leq 2.5\%$, the study is futile and further enrollment will be stopped.
- If the posterior probability of ORR $\geq 21\%$ in overall population is $\geq 80\%$ AND the posterior probability of ORR $\geq 15\%$ in CPS < 10 subpopulation is $\geq 70\%$, then early success is met and further enrollment may be stopped.
- Otherwise, the enrollment will continue as is until 40 patients.

The above decision rules for interim analysis are non-binding.

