3. ANALYSIS POPULATIONS

3.1. Full Analysis Set

The Full Analysis Set (FAS) consists of all patients who receive at least 1 full or partial dose of study treatment (DSP-7888 Dosing Emulsion, nivolumab, or pembrolizumab). Patients will be classified according to the treatment assigned (dose level and schedule).

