5.2. Standard Analysis

5.2.1. Subjects Disposition

All patients who signed pre-screened and screened informed consent will be summarized. The number and percentage of study patients will be tabulated for different analysis sets (Section 3) and by different phases and treatment information below.

Phase 1b: Arm 1, Arm 2; Overall,

Phase 2: CPS < 10, CPS >= 10, Overall

The number and percentage of patients reaching end of treatment, and end of study, along with the discontinuation reasons will be summarized as treatment assignment in phase 1b and CPS subgroups and overall in phase 2.

Listing for analysis sets and end of treatment and end of study reasons will be provided.

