5.2.6. Extent of Exposure

Dose Schedule for phase 1b part is summarized as below:

Table 5: Phase 1b Study Dose Level and Schedule

DSP-7888 Dosing Emulsion Dose Level	DSP-7888 Dosing Emulsion Dose and Schedule
DSP-7888 Dosing Emulsion Dose Level I	Nivolumab Arm (Arm 1): 10.5 mg weekly for 4 weeks for induction phase, then every 2 weeks for maintenance phase Pembrolizumab Arm (Arm 2): 10.5 mg weekly for 3 weeks for induction phase, then every 3 weeks for maintenance phase
DSP-7888 Dosing Emulsion Dose Level II	Nivolumab Arm (Arm 1): 3.5 mg weekly for 4 weeks for induction phase, then every 2 weeks for maintenance phase Pembrolizumab Arm (Arm 2): 3.5 mg weekly for 3 weeks for induction phase, then every 3 weeks for maintenance phase
DSP-7888 Dosing Emulsion Dose Level III	Nivolumab Arm (Arm 1): 1.75 mg weekly for 4 weeks for induction phase, then every 2 weeks for maintenance phase Pembrolizumab Arm (Arm 2): 1.75 mg weekly for 3 weeks for induction phase, then every 3 weeks for maintenance phase

Table 6: PD-1 Inhibitor Dose

PD1 Inhibitor	Dose and Schedule
Nivolumab	In Arm 1, 240 mg administered intravenously (IV) over 30 minutes (± 5)* every 14 days (2 weeks/cycle) starting from Day 1 of Cycle 3 (Day 29), then maintenance phase (after Cycle 3).
Pembrolizumab	In Arm 2, 200 mg/8 mL administered through IV infusion over 30 (± 5) minutes every 21 days (3 weeks) starting from Day 1 of Cycle 2 (Day 22), then maintenance phase (after Cycle 2).

*The administration time change from 60 to 30 minutes is based on the updated dosage and administration guidance of the new nivolumab product label released in July 2018.

DSP-7888 Dosing Emulsion and pembrolizumab will be administered at the recommended dose level from the Phase 1 part of the study, following the same schedule as listed in Table 10.

Table 7: Phase 2 Study Dosing Schedule

Investigational Product	Frequency	Dosage	Route of Administration
DSP-7888 Dosing Emulsion	Q1W for first 3 weeks Q3W post 3 weeks	10.5mg	Intradermal injection (ID)
Pembrolizumab	Q3W, starting from Day 1 of Cycle 2 (Day 22)	Solution for infusion 200mg/8mL	IV infusion

The dose schedules for the study have been changed under different protocol amendment. Below is a summary of the different dosing schedule:

Table 8: Planned Dose Intensity

Treatment Group	Dose Level	During Induction Phase	During Maintenance Phase
DSP-7888 Dosing Emulsion + nivolumab	Level I (10.5 mg)	10.5 mg / week	5.25 mg / week

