5.4.1. Adverse Events

Treatment-Emergent Adverse Events

An AE will be regarded as treatment-emergent, if

- it occurs for the first time on or after the first dose date of either DSP-7888 or CPI up to 30 days after the last dose of study drug; or
- it occurs up to any time if serious and considered related to study drug.

The emphasis for AE analysis will be based on treatment-emergent AE (TEAE), however all AEs will be listed.

All AEs will be coded using Medical Dictionary for Regulatory Activities (MedDRA version 20.0) and summarized by MedDRA System Organ Class and Preferred Term. The severity of all AEs will be graded by the Investigator using NCI CTCAE version 4.0.

An overview of treatment-emergent adverse events (TEAEs) will be provided. The number and percentage of subjects with following will be summarized for phase 1b, Arm 1 and Arm2 overall, phase 2: CPS < 10, CPS \geq 10 and Overall.

- Subjects with any TEAE
- Subjects with TEAE of CTCAE grade 3 or higher
- Subjects with serious adverse events (all causality and related)
- TEAEs related to study drug
- TEAEs related to study drug with CTCAE grade 3 or higher
- Subjects with TEAE leading to study drug discontinuation (all causality and related)
- Subjects with TEAE leading to study drug dose reduction (all causality and related)
- Subjects with TEAE leading to study drug dose interruption (all causality and related)

Summary of AEs by SOC and Preferred Term

The number and percentage of subjects with TEAEs by SOC, PT and maximum CTCAE grade will be summarized. A summary of TEAEs of CTCAE grade 3 or higher (Grade 3, 4, 5) will be presented by SOC and PT and maximum CTCAE grade (All Grade, \geq Grade 3).

The number and percentage of patients who experience any TEAE will be summarized by SOC and PT (All Grade, \geq Grade 3). A summary of TEAEs by PT and maximum CTCAE grade will be presented. The most commonly reported TEAEs using a different cutoff (e.g. 2% or 10% or more of patients in either arm) may also be summarized by PT as needed.

TEAEs associated with permanent discontinuation /dose reduction/drug interruption of either DSP7888 and/or CPI will be summarized by SOC and PT and maximum CTCAE Grade (taking into consideration the action taken from CRF AE page).

Treatment Related Adverse Events

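### The SAP classifies patients by dose level and schedule, but its summary columns and the Phase 2 interim rule do not separate the concurrent from the staggered schedule

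*SAP*

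**What the plan says.** **Classification.** For the Full Analysis Set, SAP 3.1 states "Patients will be classified according to the treatment assigned (dose level and schedule"). SAP 3.2 does the same for the Safety Set by treatment received. SAP 5.2.6 acknowledges that "The dose schedules for the study have been changed under different protocol amendment", and SAP Figure 1 draws two day grids for each combination.

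**Schedules.** In the completed Phase 1b dose search the PD-1 inhibitor began on Day 1. Protocol 6.1.3 gives the enrichment cohort a staggered schedule, with the vaccine alone first. In Phase 2, Protocol 6.1.4 gives Amendment 4 patients the dose-search Arm 2 schedule, and then: "For patients enrolled under Protocol Amendment 5, administration of DSP-7888 Dosing Emulsion and anti-PD1 will be staggered as follows".

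**Columns.** SAP 3.3 places the dose-search and enrichment parts in the same two arms. SAP 5.2.1 tabulates disposition as "Phase 1b: Arm 1, Arm 2; Overall" and Phase 2 by CPS subgroup and overall. SAP 5.4.1 uses the same columns for the TEAE overview, which "will be summarized for phase 1b, Arm 1 and Arm2 overall, phase 2: CPS < 10", then CPS 10 or higher and overall.

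**Phase 2 rule.** Interim monitoring "will start after the first 20 patients have response evaluation, withdraw, or die by Week 24" (SAP 2.2), without reference to schedule. SAP section 5 says Phase 2 was terminated through interim monitoring and that the final report is a synoptic, safety-focused one.

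**The concern.** The analysis sets promise a classification that the tables do not deliver. AE incidence and severity is a Phase 1b primary endpoint, and safety is now nearly all that the final report will summarise. A reader of an arm column will see one percentage for two exposures and cannot tell how much comes from each.

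The protocol itself treats schedule as consequential. Section 4.3.1.1 justifies the change by mouse data suggesting that "concomitant treatment with anti-PD-1 in suboptimal priming conditions confers resistance to immunotherapy", and section 6.4 applies the DLT criteria separately to each administration schedule. The synopsis also lists, for Phase 1b, "The incidence of treatment-emergent AEs (TEAEs) during the first 2 cycles compared with the third and subsequent cycles". That comparison means different things on the two schedules: in staggered Arm 1, Cycles 1-2 contain no nivolumab, while on the legacy schedule they contain it throughout.

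In Phase 2, the interim patients may include some on a schedule that had since been replaced. How many is not stated.

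**Working it through.** **1. The plan's own figures.** Total enrollment: 24 + 40 = 64 and 24 + 60 = 84, as stated (64-84). SAP Table 8 maintenance intensities also reproduce: 10.5/2 = 5.25 mg/week with nivolumab and 10.5/3 = 3.5 mg/week with pembrolizumab.

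**2. Early exposure, counted from SAP Figure 1** (10.5 mg per vaccine dose; windows are the DLT periods in Protocol 6.4).

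| | Vaccine days | PD-1 days | Vaccine doses (mg) | PD-1 doses |
|---|---|---|---|---|
| Arm 1, Days 1-28, concurrent | 1, 8, 15, 22 | 1, 15 | 4 (42) | 2 |
| Arm 1, Days 1-28, staggered | 1, 8, 15, 22 | none (starts Day 29) | 4 (42) | 0 |
| Arm 2, Days 1-42, concurrent | 1, 8, 15, 22, 29, 36 | 1, 22 | 6 (63) | 2 |
| Arm 2, Days 1-42, staggered | 1, 8, 15, 22 | 22 | 4 (42) | 1 |

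**3. Extent of mixing, Phase 1b.** Protocol 4.3.2 reports 13 dose-search patients as of 16 Dec 2019 (7 nivolumab, 6 pembrolizumab). I take 13 as final because the protocol says this part is completed. Enrichment plans 10. Of 13 + 10 = 23, 13/23 = 57% are concurrent and 10/23 = 43% staggered. If the true event proportions are a and b, the overall column estimates 0.57a + 0.43b. The split of the 10 between arms is the physician's choice, so the staggered share can run from 0 to 10/17 = 59% in Arm 1 and from 0 to 10/16 = 63% in Arm 2.

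**4. Extent of mixing, Phase 2.** The Amendment 4 count, k, is not given and could be small or nil. The following is illustration only, for the overall-population POC condition at n = 40. Assumptions: staggered ORR 21% (the protocol's target); legacy ORR either 8% (its reference value) or 15%; and a Beta(1,1) or Beta(0.5,0.5) prior, since the documents state none. The condition requires the posterior 10th percentile to be at least 8% and the 80th percentile at least 21%. That means 6 or more responders under Beta(1,1) and 7 or more under Beta(0.5,0.5). Responders are the sum of Binomial(k, legacy ORR) and Binomial(40 - k, 0.21).

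| Prior | Legacy ORR | k = 0 | k = 10 | k = 20 |
|---|---|---|---|---|
| Beta(1,1) | 8% | 87% | 74% | 53% |
| Beta(1,1) | 15% | 87% | 82% | 75% |
| Beta(0.5,0.5) | 8% | 76% | 58% | 36% |

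**5. Interim at 20.** The chance of no responders is 0.79^20 = 0.9% with k = 0, and 0.92^10 × 0.79^10 = 4.1% with k = 10 and legacy ORR 8%. This is not the chance of futility. The rule also requires P(ORR ≥ 15%) ≤ 2.5% in CPS < 10. Under Beta(1,1), zero responders among m such patients gives 0.85^(m+1). Even with all 20 patients CPS < 10 this is 0.85^21 = 3.3%, so the rule cannot trigger at 20. Under Beta(0.5,0.5) it needs zero responders and at least 16 CPS < 10 patients.

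**The case against.** Several objections have force.

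- **Not every decision is pooled.** DLT incidence excludes the enrichment cohort, and the Dose-Determining Set is limited to dose search (Protocol 12.1.2.3). The recommended-dose decision rests on the concurrent schedule alone. The protocol also summarises the PFS ratio for the enrichment cohort separately. This stands.
- **The data are not hidden.** AEs, ISRs, deaths and responses are all listed. A reader might infer that neither regimen's safety or activity can be read; the documents support only that they are not summarised by schedule.
- **Exposure is partly handled.** DSP-7888 exposure is also split by induction and maintenance, planned doses follow the protocol-defined schedule, and PD-1 exposure runs from the first PD-1 dose. This stands, although the summaries still lack a schedule column.
- **No dilution of a rate over time.** TEAE tables count patients with an event, not events per unit time, so vaccine-only weeks do not by themselves lower the percentages. The mouse rationale concerns resistance and does not predict different toxicity. Both points stand. The case rests on the exposure difference in the table above, not on a demonstrated toxicity difference.
- **The Cycle 1-2 comparison appears only in the protocol.** SAP 5.4.1 contains no such table, so there is no SAP split to replace.
- **Phase 2 is over.** The final POC analysis will not be run, and the interim rule was non-binding. A reader might infer that patients on the replaced schedule stopped the current one. The documents do not show this: k is unknown, and zero responders is not the futility rule.
- **Schedule columns would not isolate the regimen.** In Phase 1b, dose search took mixed tumours, some patients being stable on PD-1 therapy; enrichment took RCC or urothelial cancer that had progressed on it. This stands and limits what the columns can show.

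None of this answers the central point that sections 3.1 and 3.2 classify by schedule and the columns do not.

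**Conclusion.** The point holds as an unexecuted classification. The Phase 1b arm and overall columns blend about 13 concurrent and 10 planned staggered patients (57% and 43%) whose early PD-1 exposure, and in Arm 2 vaccine exposure, differ materially. Because the final report is essentially a safety report, this affects how a primary endpoint is presented. The DLT and recommended-dose conclusions are untouched.

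For Phase 2 the defect is that the columns and the interim rule do not distinguish schedules. Its size cannot be computed without the Amendment 4 count. The POC percentages are illustrations of one of two alternative conditions, under an assumed prior, legacy count and legacy ORR. At k = 20 under Beta(1,1) they run from 53% to 75% depending only on the legacy ORR assumed. They do not show that the termination decision was wrong.

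This should be corrected before the final tables are produced.

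**What to change.** - **SAP 3.3, 5.2.1, 5.2.6 and 5.4.1, including the ISR tables:** add descriptive columns by schedule (concurrent legacy; staggered) beside the pooled column, for each Phase 1b arm and for Phase 2.
- **SAP 3.3:** state where a staggered patient who stops before the first PD-1 dose is counted. Arm membership now requires at least one dose of both drugs, so such a patient fits neither arm.
- **SAP 5.4.1:** for staggered patients, show TEAEs with onset before, and on or after, the first PD-1 dose.
- **SAP 5.5 and the report:** give the number of Phase 2 patients, and of the interim patients, on each schedule, with the response listing and a descriptive ORR by schedule. Do not add a separate POC or futility conclusion for one schedule, which would now be post hoc.

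**Cost:** additional columns derived from dosing dates already collected, with no new data or patients. Cells will be small (7 and 6 concurrent patients by arm, and 10 staggered shared between arms). The text should say that Phase 1b schedule coincides with tumour type and prior PD-1 resistance, so the columns describe each group and do not estimate a regimen effect.

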Particular attention should be given to the follow up of any **Grade 3 or higher** injection site reactions ongoing at the End of Treatment period until resolution, return to baseline, determined to be a stable or chronic condition or until the patient is lost to follow up or the patient has died. Please record the data within EDC per eCRF instructions. In the instance of resolution with sequelae, please be sure to enter the sequelae as a separate AE (eg skin discoloration, persistent induration, scarring “from ISR”). To facilitate this careful follow up, please consider use of video teleconference with the patient during the follow up period post study.

Objective disease assessments will be performed according to RECIST and iRECIST. For Phase 1b, the first assessment will be performed during Cycle 3, at 4 weeks for the nivolumab arm and at 6 weeks for the pembrolizumab arm, and at Weeks 12, 18, and 24, after the first dose of DSP-7888 Dosing Emulsion. After that, objective disease assessments will occur every 12 weeks until patient discontinuation from the study. For Phase 2, patients will be evaluated for objective response to study drug treatment with radiographic imaging every 6 weeks for 24 weeks and then every 12 weeks until progression.

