### **8.3.5. Evaluation and Management of Injection Site Reactions**

#### **8.3.5.1. Evaluation of Injection Site Reactions**

The type of ISR should be reported for the AE verbatim term (eg injection site redness should be reported as injection site redness, and not injection site reaction). Injection site reactions will be graded according to CTCAE v4.03 ([Table 11](#)).

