#### **8.5. Prior and Concomitant Therapy**

Patients should receive treatment for all inter-current medical conditions or AEs at the discretion of the investigator in conformance with community or institutional medical standards.

All information regarding concomitant treatments (medications or procedures) must be recorded on the patient's case report form/electronic case report form (CRF/eCRF) (including the name of the medication or procedure and duration of treatment).

Palliative and supportive care for disease-related symptoms will be offered to all patients in this study. Patients may receive palliative radiation therapy or palliative surgery for symptomatic lesion(s) as long as the lesion is not the only evaluable one.

Study drug administration should be interrupted during and following these therapies until the patient has adequately recovered from the effects of treatment, as judged by the treating investigator.

Patients on the study will be permitted to receive COVID-19 vaccinations that are authorized for use by the Health Authorities of the country/region.

If possible, a COVID-19 vaccination should be administered on non-study drug injection days. Because DSP-7888 Dosing Emulsion is a peptide vaccine, the COVID-19 vaccine should be administered preferably 48 hours after the DSP-7888 Dosing Emulsion administration to avoid confounding of immediately occurring AEs. The COVID-19 vaccine should also be given at a different injection site from the DSP-7888 Dosing Emulsion injection site.

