Treatment-related TEAEs are those judged by the investigator to be at least possibly related to the study drugs (DSP7888 and/or CPI) or for which relatedness is recorded as “unknown” by the investigator. Treatment related will include “possible”, “probable” or “definite” causality assessments. Missing relationship will be considered as “Related” to all drugs received by the patient. Similar summaries as noted for all causality TEAEs will be provided for treatment related TEAEs.

Serious Adverse Events and Death

Treatment-emergent SAEs and Treatment-related SAEs will be summarized by MedDRA SOC and PT and maximum CTCAE grade.

TEAE leading to death will be summarized by MedDRA SOC and Preferred Term.

Deaths will be summarized by on study and on treatment (within 30 days of last dose of study medication). The number and percentage of patients who died on study and on treatment, as well as primary cause of death will be summarized. Deaths may also be categorized according to time of occurrence after first dose.

A listing of death data will also be provided and will include all deaths that occurred from the signing of the informed consent to the end of the follow up period. The listing will include primary cause of death and the number of days relative to the administration of first and last dose.

Adverse Events of COVID-19

Preferred Terms corona virus infection and coronavirus test positive will be used to identified COVID-19 positive cases in adverse event.

Injection Site Reaction (ISR)

The predominant adverse effect observed with DSP-7888 is injection site reaction. The Preferred Terms of TEAEs within the High Level Group Term of “Administration Site Reaction” (MedDRA version 20.0) will be used to identify events of injection site reaction.

Below analysis will be provided for ISR:

- ISR by SOC, PT, and maximum CTCAE Grade
- Onset time of first ISR for patients with at least one ISR: Time to onset is analyzed for patients with at least one ISR from the first dose of the DSP-7888 to the first occurrence of ISR regardless of CTCAE grade.
- Onset time of first ISR: Time to first ISR is defined as the time from the first dose of the DSP-7888 to the first occurrence of ISR . For patients with no ISR, the onset time will be censored as data cutoff date,

end of study date, death date, or safety follow-up completion date (end of treatment date + 30 days) whichever is shorter.

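### SAP 5.4.1 selects injection site reactions by a term group for any administration site, with no link to DSP-7888, so local reactions to other products can be counted as DSP-7888 reactions

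*SAP*

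**What the plan says.** SAP 5.4.1 opens its ISR block by tying the event to the vaccine: "The predominant adverse effect observed with DSP-7888 is injection site reaction". The selection rule comes next: "The Preferred Terms of TEAEs within the High Level Group Term of “Administration Site Reaction” (MedDRA version 20.0". Nothing further limits the set. The onset analysis is anchored to DSP-7888: "Time to first ISR is defined as the time from the first dose of the DSP-7888 to the first occurrence of ISR". The same origin serves time to first Grade 3 or higher ISR. The block also plans a table by system organ class, preferred term and maximum grade, a listing, and an optional duration analysis.

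Two other definitions in SAP 5.4.1 feed this set or might have narrowed it. The treatment-emergent window opens with either drug: an event qualifies if "it occurs for the first time on or after the first dose date of either DSP-7888 or CPI". Treatment-relatedness is pooled, covering events judged "at least possibly related to the study drugs (DSP7888 and/or CPI"), and the ISR rule does not use it.

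The protocol gives no formal definition of ISR and no MedDRA grouping. Its uses of the term concern DSP-7888: sections 4.3.4, 6.4, 8.3.1, 8.3.2 and 8.3.5. Section 8.3.5.1 asks for specific wording: "The type of ISR should be reported for the AE verbatim term". Section 8.5 says: "Patients on the study will be permitted to receive COVID-19 vaccinations that are authorized for use".

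**The concern.** The ISR summaries are introduced as a description of one product's local toxicity, but the rule is worded for any administration site. A patient with a local reaction only where the PD-1 inhibitor was infused, or only where a COVID-19 vaccine was given, could be tabulated as having a DSP-7888 ISR.

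At stake are ISR incidence by grade and the two time-to-first-event summaries. They carry weight because SAP sections 5, 5.5 and 5.6 limit the final report to safety, without efficacy or biomarker analyses. The denominators are also small.

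**Working it through.** The plan states no ISR rate or count, so there is no figure to reproduce. The check is a reading of the rule against the trial's design, followed by an illustration of size.

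**1. What the rule requires.** An event enters the set if it is treatment-emergent and its preferred term lies in the named group. Product, route, body site and causality play no part.

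**2. Whether other administration sites exist.** They do, by design.
- PD-1 inhibitor: intravenous, every 2 weeks (nivolumab) or every 3 weeks (pembrolizumab), per protocol Table 5 and section 6.1.4.4.
- COVID-19 vaccine: permitted, preferably 48 hours after DSP-7888 and at a different site (protocol 8.5). The stated reason is to keep immediate adverse events from being confounded. The protocol thus recognises the problem, while the SAP rule makes no use of that separation.

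**3. Whether a later step repairs it.**
- Table by preferred term: in part. A term that names an infusion site would show on its own row. A COVID-19 vaccine reaction coded to an injection-site term would not stand apart.
- Onset summaries: no. They pool all terms.
- Relatedness: no. It is pooled over both study drugs and is not applied here.

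**4. When a result would actually change.** Any-grade incidence moves only if the patient has no DSP-7888 ISR. Grade 3 or higher incidence moves only if the other-site reaction is itself Grade 3 or higher and the patient has no such DSP-7888 event. Time to first ISR moves only if the other-site reaction comes first, or stands alone.

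**5. Size.** Let p be the share of patients with a DSP-7888 ISR, and q the share of the remainder with only a reaction at another site. The rise in reported any-grade incidence is (1 − p) × q. Neither value is in the documents. I assume p from 60% to 80% and q from 2% to 10%, with 40 Phase 2 patients:
- Low: (1 − 0.80) × 0.02 = 0.004, or 0.4 points; 0.004 × 40 = 0.16 patients.
- High: (1 − 0.60) × 0.10 = 0.040, or 4.0 points; 0.040 × 40 = 1.6 patients.

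One patient whose status does change is worth 1/40 = 2.5 points, 1/20 = 5 points at the interim-monitoring size, and 1/7 = 14.3 or 1/6 = 16.7 points in the dose-search arms (7 and 6 patients per protocol 4.3.2). These are weights per patient; they do not show that any patient is misclassified.

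**The case against.** The strongest defence is that a broad set that ignores causality is a reasonable safety choice. It misses little and errs towards over-counting harm, and the analyses are descriptive with no formal hypothesis (SAP 2.1). The table by preferred term and the listing let a reader set some events aside.

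The schedule helps too. Under Amendment 5 the PD-1 inhibitor starts on Day 22 or Day 29, after 3 or 4 weekly DSP-7888 doses. At six injection sites per 10.5 mg dose (protocol Table 10), that is 3 × 6 = 18 or 4 × 6 = 24 intradermal injections before the first infusion day. An infusion-site event is then unlikely to set time to first ISR.

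Much of this stands. It lowers the likely size, and the sensitivity argument shapes the fix. It does not remove the defect: patients on the legacy schedule started both drugs on Day 1, and the onset summaries cannot be unpicked by term.

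Two stronger readings go beyond the documents.

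- A reader might infer that infusion-site and vaccine-site reactions necessarily count as ISRs. Neither document lists the terms in the group, so the text supports only that they can. Nothing shows that systemic infusion reactions would be captured.
- A reader might infer that lasting skin damage drops out, because protocol 6.1.4.5 tells sites: "please be sure to enter the sequelae as a separate AE (eg skin discoloration, persistent induration, scarring". That sentence goes on to attach the words *from ISR*, section 8.3.5.1 asks for specific verbatim terms, and neither document says how sequelae are coded. A sequela also follows an ISR that has already occurred, so incidence and time to first ISR would not change. All adverse events are listed in any case.

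**Conclusion.** The point holds as a gap in an event definition: the SAP's rule lacks the link to DSP-7888 that its own framing and time origin imply, so reactions at other sites can enter the ISR results. The size is unknown and probably small. The 0.4 to 4.0 points above rest entirely on assumed rates and on 40 patients. Phase 2 was stopped on interim monitoring, so the final number may be lower.

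Two readings of its importance should be resisted. A reader might infer that these are the only product-specific analyses left in the report, but SAP 5.2.6.1 to 5.2.6.3 summarise exposure by drug. A reader might also reckon that one stray Grade 3 case added to two to four true cases inflates the count by 1/4 = 25% to 1/2 = 50%. The arithmetic is right, but both counts are invented, and nothing in the documents suggests that an infusion or a COVID-19 vaccine caused such an event here.

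This is a modest correction, worth making because it is cheap.

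**What to change.** In SAP 5.4.1, keep the administration-site group as the search and add a second step. Remove from the ISR set:

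- events whose term names an infusion or catheter site; and
- events whose verbatim term or recorded causality attributes them only to the PD-1 inhibitor or to another product, such as a COVID-19 vaccine.

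Otherwise keep injection-site, vaccination-site and unspecified administration-site terms. DSP-7888 is itself a peptide vaccine (protocol 4.2), so dropping all vaccination-site terms could discard its own reactions. Restricting to injection-site terms alone would not be enough either, since a COVID-19 vaccine reaction may be coded to one. Do not require a positive relatedness rating, which would lose true reactions that the investigator rated unlikely or unrelated.

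List the removed events and report the unrestricted group as a sensitivity summary. If wanted, flag in the ISR listing any adverse event whose verbatim term carries the words *from ISR*.

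The cost is SAP wording, a short term review done without sight of outcomes, and slightly lower sensitivity, which the sensitivity summary makes visible. The SAP treats a missing relationship as related to all drugs received, which suggests that causality is recorded per drug. The documents do not show whether attribution to a COVID-19 vaccine is recorded; if it is not, the verbatim term must serve.
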